# Clinical Laboratory Evaluations: Coagulation Normal Ranges

Parameter	Gender	Age (Years)	Low - High
PTT	_	18 - 65+	22 - 34
INR	_	18 - 65+	0.9 - 1.1
PT	_	18 - 65+	9 - 11.5

Ranges are given for adults (age at least 18 years).

Age (Years) = "18 - 65+" indicates that there is no restriction on normal due to age in adults.

Listing 16.2.8.4
Clinical Laboratory Evaluations: Urinalysis

Site/ Subject	Treatment	Visit	Day	Date	Laboratory Parameter (Units)	Value
xxx/xxxx	XXXXX	Pre-Study		MM/DD/YYYY	XXXXXXXXXXXXXXXXXXXXXXXXXXXXXXXXXXXXXX	XXX
					XXXXXXXXXXXXXXXXXXXXXXXXXXXXXXXXXXXXXX	XXX
					XXXXXXXXXXXXXXXXXXXXXXXXXXXXXXXXXXXXXX	XXX
		Baseline		MM/DD/YYYY	XXXXXXXXXXXXXXXXXXXXXXXXXXXXXXXXXXXXXX	XXX
					XXXXXXXXXXXXXXXXXXXXXXXXXXXXXXXXXXXXXX	XXX
					XXXXXXXXXXXXXXXXXXXXXXXXXXXXXXXXXXXXXX	XXX
		Cycle 1	8	MM/DD/YYYY	XXXXXXXXXXXXXXXXXXXXXXXXXXXXXXXXXXXXXX	XXX
					XXXXXXXXXXXXXXXXXXXXXXXXXXXXXXXXXXXXXX	XXX
					XXXXXXXXXXXXXXXXXXXXXXXXXXXXXXXXXXXXXX	XXX
		Cycle 1	15	MM/DD/YYYY	XXXXXXXXXXXXXXXXXXXXXXXXXXXXXXXXXXXXXX	XXX
					XXXXXXXXXXXXXXXXXXXXXXXXXXXXXXXXXXXXXX	XXX
					XXXXXXXXXXXXXXXXXXXXXXXXXXXXXXXXXXXXXX	XXX
		Cycle 2	1	MM/DD/YYYY	XXXXXXXXXXXXXXXXXXXXXXXXXXXXXXXXXXXXXX	XXX
					XXXXXXXXXXXXXXXXXXXXXXXXXXXXXXXXXXXXXX	XXX
					XXXXXXXXXXXXXXXXXXXXXXXXXXXXXXXXXXXXXX	XXX
		Cycle 2	15	MM/DD/YYYY	XXXXXXXXXXXXXXXXXXXXXXXXXXXXXXXXXXXXXX	XXX
					XXXXXXXXXXXXXXXXXXXXXXXXXXXXXXXXXXXXXX	XXX
					XXXXXXXXXXXXXXXXXXXXXXXXXXXXXXXXXXXXXX	XXX
		Cycle 3	1	MM/DD/YYYY	XXXXXXXXXXXXXXXXXXXXXXXXXXXXXXXXXXXXXX	XXX
					XXXXXXXXXXXXXXXXXXXXXXXXXXXXXXXXXXXXXX	XXX
					XXXXXXXXXXXXXXXXXXXXXXXXXXXXXXXXXXXXXX	XXX

Baseline=Cycle 1 Day 1 (or Pre-Study if <= 3 days prior to Cycle 1 Day 1 or if value at Cycle 1 Day 1 is missing)

Programming Notes: Continue for all cycles, Days 1 and 15. CFB is not computed for any urinalysis parameter.

Listing 16.2.8.5 Clinical Laboratory Evaluations: Thyroid Function

				T3 (U	nit)	T4 (U	nit)	TSH (I	Jnit)
Site/ Subject	Treatment	Visit	Date	Value (1)	CFB	Value (1)	CFB	Value (1)	CFB
xxx/xxxx	XXXXX	Pre-Study	MM/DD/YYYY	XXX		XXX		XXX	
		Cycle 1	MM/DD/YYYY	XXX		XXX		XXX	
		Cycle 2	MM/DD/YYYY	XXX	XXX	XXX	XXX	XXX	XXX
		Cycle 3	MM/DD/YYYY	XXX	XXX	XXX	XXX	XXX	XXX
xxx/xxxx	xxxxx	Pre-Study	MM/DD/YYYY	XXX		XXX		xxx	
		Cycle 1	MM/DD/YYYY	XXX		XXX		XXX	
		Cycle 2	MM/DD/YYYY	XXX	XXX	XXX	XXX	XXX	XXX
		Cycle 3	MM/DD/YYYY	XXX	xxx	XXX	XXX	XXX	XXX

 H=Abnormal High, L =Abnormal Low

Normal ranges are given at the end of the listing. CFB=Change from Baseline

Baseline=Cycle 1 (or Pre-Study if <= 3 days prior to Cycle 1 Day 1 or if value at Cycle 1 Day 1 is missing)

Programming Notes: Continue for all cycles. Include units. Column for "Day" deleted since Thyroid Function assessed only at Day 1.

Listing 16.2.8.5 Clinical Laboratory Evaluations: Thyroid Function Normal Ranges

Parameter	Gender	Age (Years)	Low - High
T3	_	18 - 65+	3.5 - 6.5
T4	_	18 - 65+	10.3 - 23.2
TSH	-	20+	0.4 - 4.5

Ranges are given for adults (age at least 18 years).

Age (Years) = "18 - 65+" indicates that there is no restriction on normal due to age in adults.

**Listing 16.2.8.6**Pregnancy Test

Site/ Subject	Treatment	Visit	Test Date	Result	Not Done?	Not Applicable?	Menopausal date/ Other Specify
xxx/xxxxx	XXXXX	Pre-Study	DD/MM/YY	XXXX		• •	
		Cycle 1	DD/MM/YY	XXXX			
		Cycle 2	DD/MM/YY		XXXX		
		Cycle 3	DD/MM/YY	XXXX			
xxx/xxxxx	XXXXX	Pre-Study	DD/MM/YY			XXXX	
		Cycle 1	DD/MM/YY			XXXX	
		Cycle 2	DD/MM/YY			XXXX	
		Cycle 3	DD/MM/YY			XXXX	

Programming Note: Continue for all cycles. For "Not Applicable?", enter reason if not applicable.

Listing 16.2.9.1

Vital Signs

				Systol		Diasto			Femperat		Respirat	•	Pu	
				(mm	Hg)	(mm	ıHg)		(degrees	C)	(/m	nin)	(beats	s/min)
Site/ Subject	Treatment	Visit	Time	Value	CFB	Value	CFB	Value	CFB	Method	Value	CFB	Value	CFB
xxx/xxxxx	XXXX	Pre-Study		XXX		XXX		XXX		Х	XXX		XXX	
		Cycle 1	Day 1	XXX		XXX		XXX		X	XXX		XXX	
			Day 1 Hour 1	XXX	XXX	XXX	XXX	XXX	XXX	X	XXX	XXX	XXX	XXX
			Day 1 Hour 2	xxx	XXX	XXX	XXX	XXX	XXX	Х	XXX	XXX	XXX	XXX
			Day 8	XXX	xxx	xxx	xxx	xxx	xxx	х	xxx	xxx	xxx	XXX
			Day 15	XXX	XXX	XXX	XXX	XXX	XXX	X	XXX	XXX	XXX	XXX
		Cycle 2	Day 1	XXX	XXX	XXX	XXX	XXX	XXX	X	XXX	XXX	XXX	XXX
			Day 15	XXX	XXX	XXX	XXX	XXX	XXX	X	XXX	XXX	XXX	XXX
		Cycle 3	Day 1	XXX	XXX	XXX	XXX	XXX	XXX	X	XXX	XXX	XXX	XXX
			Day 15	XXX	XXX	XXX	XXX	XXX	XXX	X	XXX	XXX	XXX	XXX

CFB=Change from Baseline Baseline=Cycle 1 Day 1 (or Pre-Study if value at Cycle 1 Day 1 is missing) Method= 'O' for oral, 'A' for Axillary

Programming Note: Continue for all visits (Days 1 and 15 of each cycle, Day 8 of Cycle 1, and Hours 1, 2, 3, 4, 6 and 8 on Cycle 1 Day 1) with CFB.

Listing 16.2.9.2 Weight, Height, and BMI

					Weigh	nt (kg)	BMI (k	g/m^2)
Site/ Subject	Treatment	Visit	Time	Height (cm)	Value	CFB	Value	ĆFB
xxx/xxxxx	XXXX	Pre-Study		XXX	XXX		XXX	
		Cycle 1	Day 1		XXX		XXX	
			Day 8		XXX	XXX	XXX	XXX
			Day 15		XXX	XXX	XXX	XXX
		Cycle 2	Day 1		XXX	XXX	XXX	XXX
			Day 15		XXX	XXX	XXX	XXX
		Cycle 3	Day 1		XXX	XXX	XXX	XXX
			Day 15		XXX	XXX	XXX	XXX
xxx/xxxxx	XXXX	Pre-Study		XXX	XXX		XXX	
		Cycle 1	Day 1		XXX		XXX	
			Day 8		XXX	XXX	XXX	XXX
			Day 15		XXX	XXX	XXX	XXX
		Cycle 2	Day 1		XXX	XXX	XXX	XXX
			Day 15		XXX	XXX	XXX	XXX
		Cycle 3	Day 1		XXX	XXX	XXX	XXX
			Day 15		XXX	XXX	XXX	XXX

CFB=Change from Baseline
Baseline=Cycle 1 Day 1 (or Pre-Study if <= 3 days prior to Cycle 1 Day 1 or if value at Cycle 1 Day 1 is missing)
BMI=Body mass index.

BMI is computed using Height recorded at Pre-Study.

Programming Note: Continue for all cycles.

Listing 16.2.9.3 **ECOG Performance Status** 

			Assessment		CFB
Site/ Subject	Treatment	Visit	Date	ECOG PS	ECOG PS
xxx/xxxxx	XXXX	Pre-Study	DD/MM/YY	XXX	
		Cycle 1	DD/MM/YY	XXX	
		Cycle 2	DD/MM/YY	XXX	XXX
		Cycle 3	DD/MM/YY	XXX	XXX
		Cycle 4	DD/MM/YY	XXX	XXX
xxx/xxxxx	XXXX	Pre-Study	DD/MM/YY	XXX	
		Cycle 1	DD/MM/YY	XXX	
		Cycle 2	DD/MM/YY	XXX	XXX
		Cycle 3	DD/MM/YY	XXX	XXX
		Cycle 4	DD/MM/YY	XXX	XXX

CFB=Change from Baseline
Baseline=Cycle 1 Day 1 (or Pre-Study if <= 3 days prior to Cycle 1 Day 1 or if value at Cycle 1 Day 1 is missing)

PS = Performance Status

0=Normal activity, 1=Symptoms but ambulatory, 2= In bed <50% of time, 3=In bed >50% of time, 4=100% bedridden

Programming Notes: Continue for all cycles. Record CFB as Decrease, No Change, or Increase.

Listing 16.2.10.1

Electrocardiogram (ECG) – Continuous Variables

											Interva	al (msec)			
						Heart (bp		Р	R	QF	RS	Q 	Γ	QTcF	<del>-</del> (1)
Site/															
Subject	Treatment	Visit	Day	Hour	Time	Value	CFB	Value	CFB	Value	CFB	Value	CFB	Value	CFE
xxx/xxxxx	XXXXXXX	Pre-Study			XX:XX	XX		XX		XX		XX		XX	
		Cycle 1	1	0	XX:XX	XX		XX		XX		XX		XX	
				2	XX:XX	XX	XX	XX	XX	XX	XX	XX	XX	XX	XX
				4	XX:XX	XX	XX	XX	XX	XX	XX	XX	XX	XX	XX
				6	XX:XX	XX	XX	XX	XX	XX	XX	XX	XX	XX	XX
			8	0	XX:XX	XX	XX	XX	XX	XX	XX	XX	XX	XX	XX
				2	XX:XX	XX	XX	XX	XX	XX	XX	XX	XX	XX	XX
				4	XX:XX	XX	XX	XX	XX	XX	XX	XX	XX	XX	XX
				6	XX:XX	XX	XX	XX	XX	XX	XX	XX	XX	XX	XX
			15	0	XX:XX	XX	XX	XX	XX	XX	XX	XX	XX	XX	XX
		Cycle 2	1	0	XX:XX	XX	XX	XX	XX	XX	XX	XX	XX	XX	XX
		-	15	0	XX:XX	XX	XX	XX	XX	XX	XX	XX	XX	XX	XX
		Cycle 3	1	0	XX:XX	XX	XX	XX	XX	XX	XX	XX	XX	XX	XX
			15	0	XX:XX	XX	XX	XX	XX	XX	XX	XX	XX	XX	XX

Hour 0=Pre-Dose

CFB=Change from Baseline

Baseline=Cycle 1 Day 1 Hour 0 (or Pre-Study if the value at Cycle 1 Day 1 is missing)

(1) QTcF=QT Correction: Fridericia.

Programming Notes: Continue for QRS Complex (msec), PR Interval (msec), and QTcF (msec) in that order and all visits (Pre-Study, Predose on Days 1 and 15 of all cycles, Pre-dose on Day 8 of Cycle 1, and at 2, 4, and 6 hours post-dose on Days 1 and 8 of Cycle 1) with CFB. Compute QTcF=QT\*(HR/60)1/3.

Listing 16.2.10.2

Electrocardiogram (ECG) – Categorical Variables

						Overall		Cardiac
Site/ Subject	Treatment	Visit	Day	Hour	Time	Impression (1)	ST Segment	Rhythm
xxx/xxxxx	XXXX	Pre-Study				XX	XX	XX
		Cycle 1	1	0	XX:XX	XX	XX	XX
				2	XX:XX	XX	XX	XX
				4	XX:XX	XX	XX	XX
				6	XX:XX	XX	XX	XX
			8	0	XX:XX	XX	XX	XX
				2	XX:XX	XX	XX	XX
				4	XX:XX	XX	XX	XX
				6	XX:XX	XX	XX	XX
			15	0	XX:XX	XX	XX	XX
		Cycle 2	1	0	XX:XX	XX	XX	XX
			15	0	XX:XX	XX	XX	XX
		Cycle 3	1	0	XX:XX	XX	XX	XX
		-	15	0	XX:XX	XX	XX	XX

Programming Note: Continue for all visits (Pre-Study, Pre-dose on Days 1 and 15 of all cycles, Pre-dose on Day 8 of Cycle 1, and at 2, 4, and 6 hours post-dose on Days 1 and 8 of Cycle 1).

(1) 1=Normal, 2=Abnormal Not Clinically Significant, 3= Abnormal Clinically Significant Hour 0 = Pre-Dose

Listing 16.2.11.1
Physical Examination at Pre-Study Visit

Site/ Subject	Treatment	Body System	Result	Description If 'Abnormal'
xxx/xxxxx	XXXXX	General Appearance	Normal	
		Head and Neck	Normal	
		Eyes, Ears, Nose, Throat	Abnormal	XXXXX
		Skin	Normal	
		Chest / Lungs / Breast	Normal	
		Heart	Normal	
		Abdomen	Abnormal	XXXXX
		Genitourinary	Normal	
		Extremities	Normal	
		Musculoskeletal	Normal	
		Lymph Nodes	Abnormal	XXXXX
		Neurological	Normal	
		Other	Normal	XXXXX
xxx/xxxxx	XXXXX	General Appearance	Normal	
		Head and Neck	Normal	
		Eyes, Ears, Nose, Throat	Normal	
		Skin	Normal	
		Chest / Lungs / Breast	Normal	
		Heart	Not Done	
		Abdomen	Normal	
		Genitourinary	Normal	
		Extremities	Normal	
		Musculoskeletal	Normal	
		Lymph Nodes	Abnormal	XXXXX
		Neurological	Normal	
		Other	Not Done	

Programming Note: Record result as 'Normal', 'Abnormal', or 'Not Done'

**Listing 16.2.11.2**Physical Examination

			Screening <= 3 days from	Clin, Sig,			Description If different From
Site/ Subject	Treatment	Visit	Baseline?	Changes (1)	Body System	Result	Previous Assessment
xxx/xxxxx	XXXXX	Cycle 1 Day 1	No	No			
		Cycle 1 Day 8		No			
		Cycle 1 Day 15		No			
		Cycle 2 Day 1		Yes	Eyes, Ears, Nose, Throat	Abnormal	XXXXX
		•		Yes	XXXXXXXXXXXXX	XXXXXX	xxxxxxxxxxxx
		Cycle 2 Day 15		No			
		Cycle 3 Day 1		Yes	Lymph Nodes	XXXXXX	XXXXX
		Cycle 3 Day 15		No			
		Cycle 4 Day 1		No			
xxx/xxxxx	xxxxx	Cycle 1 Day 1	Yes				
		Cycle 1 Day 8		No			
		Cycle 1 Day 15		No			
		Cycle 2 Day 1		Yes			

 Are there any clinically significant changes from the physical examination conducted at the previous assessment? Baseline=Cycle 1 Day 1

Programming Notes: Continue for other cycles. If there are 'No' clinically significant changes from the physical examination conducted at the previous assessment, then the assessments for individual body systems should not be completed.

If "Clin, Sig, Changes" = 'Yes', then results should be recorded for at least one body systems with a "Result" differing from the previous assessment list. If "Screening <= 3 days from Baseline?" is Yes, there should be no responses for Cycle 1 Day 1.

Listing 16.2.12 **Prior and Concomitant Medications** 

Site/ Subject	Treatment	Medication	ATC Level 3	Reason for Use	AE no. (1)	Dose & Units	Regimen	Route (2)	Start Date Stop Date (3)
xxx/xxxxx	XXXXX	XXXX	XXXX	XXXXX	Х	XXXX	XXXX	XX	DD/MM/YY
xxx/xxxxx	xxxxx	XXXX	xxxx	xxxxx	x	xxxx	xxxx	xx	DD/MM/YY DD/MM/YY DD/MM/YY
xxx/xxxxx	xxxxx	xxxx	xxxx	XXXXX	х	xxxx	xxxx	xx	DD/MM/YY O

Includes medications taken within 30 days prior to Screening Visit.

Programming Note: Sort by start date for each subject.

 Blank if Not Applicable
(2) 1=PO; 2=IV; 3=SC; 5=IM; 11=T; 12=OU,OS,OD; 13=AU,AS,AD; 14=IN; 15=PV; 16=PR; 24=SL; 30=BUC; 37=IA; 71=NG; 136=INH; 358=TD; 135=Other; 139= Unknown

 O=Ongoing

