Hepatitis B/C virus serology	X						
Hepatitis B/C viral load (if seropositive)		X		X ⁱ		X ⁱ	
Tumor imaging for RECIST	X ^j			X ^j		X	
Concomitant medications	X	X	X	X	X	X	X
Adverse events		X	X	X	X	X	X
Dispense study drug supplies		X		X			
Review treatment compliance		X	X	X	X	X	

Trial Procedures	Pre-Study (-28 Days)	Cycle 1		Subsequent Cycle		End of Study/End of Dosing (EOS) ¹	Follow-up (28 ± 3 Days Post EOS)
		Day 1 Baseline	Days 8 and 15 ±2 Days	Day 1 ±2 Days	Day 15 ±2 Days	Day 1 ± 2 Days	

- a. Complete PE performed at the Pre-Study (and/or the Baseline Visit if performed > 3 days prior to first dose) and End of Study/End of Dosing (EOS) visits.
- b. Symptom-directed examination.
- c. If Pre-Study assessment was performed ≤ 3 days prior to the Baseline Visit, assessments do not need to be repeated.
- d. Temperature, pulse, respiration, blood pressure at: Pre-Study; pre-dose at all visits; at 1, 2, 3, 4h (± 5 min), 6 and 8h (± 10 min) post-dose on Cycle 1 Day 1 and at Follow-up.
- e. See list of parameters in [Section 9.2.8](#) and [Appendix D](#).
- f. ECG at Pre-Study; pre-dose at all visits; and at 2, 4, and 6h (± 10 min) post-dose on Cycle 1 Days 1 and 8; and at Follow-up.
- g. Performed at Pre-Study, prior to the first dose, Day 1 of each cycle, and at Follow-up.
- h. Day 1 of odd-numbered cycles, unless waived by the Sponsor (selected sites only).
- i. For subjects with measurable viral load at the Baseline Visit; on Day 1 of odd-numbered cycles only and at EOS.
- j. CT scan or MRI at Pre-Study, the end of Cycle 2, and at the end of subsequent even-numbered cycles. For trial eligibility purposes, a scan performed ≤ 21 days prior to the Pre-Study Visit may be used (allowed time window is of -7days/+1 day with respect to day 28 of each even numbered cycles; if performed at +1 day after day 28, CT/MRI scan must be performed before administration of the morning dose of that day).
- k. Sparse sampling on Day 1 of Cycles 1 and 2 only. Pre-dose trough sample on Cycle 1 Days 8 and 15 only. See [Table 10–1](#) for PK sampling time points.
- l. End of Study visit timeframe is of 2 days since the last administered dose of IMP/matching Placebo.

Table 1–2: Schedule of Events for Open Label (OL) Treatment

Trial Procedures	OL Cycle 1		Subsequent OL Cycle		OL End of Study/End of Dosing (EOS) ^j	OL Follow-up (28 ± 3 Days Post EOS)
	Day 1 Baseline	Days 8 and 15 ± 2 Days	Day 1 ± 2 Days	Day 15 ± 2 Days	Day 1 ± 2 Days	

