#### 7. STATISTICAL CONSIDERATIONS AND DATA ANALYSIS

Tables and data listings will be prepared using SAS Version 9.0 or higher. A subject's Baseline value for a specified variable will be the measurement for that variable taken on Day 1 of Cycle 1, unless the pre-study assessment was performed within 3 days prior to baseline. In the latter case, assessments do not need to be repeated prior to initiation of dosing for Physical Examination, Body Weight, Clinical Laboratory testing, Pregnancy Test, and ECOG PS, as noted in the Schedule of Procedures in Section 5 and the Baseline value will be the value at Screening.

For any variable with Change From Baseline (CFB) calculated, CFB will be calculated as CFB = Value at Post-Baseline visit – Value at Baseline.

If the final pre-treatment assessment was performed at Screening, prior to Baseline, then CFB is defined as the difference between the value at the post-Baseline visit and the value at Screening.

Simple descriptive statistics for continuous data are: n (number of non-missing observations), mean, standard deviation, maximum, median, and minimum. Categorical data will be summarized by the number and percentage of subjects in each category. The data will be summarized upon completion of the final subject. All data collected for the OL period will be listed and select variables will be summarized. Listings and summaries for the OL period will be presented separately and a separate SAP will be prepared. The following pertains to the analyses and summaries for the DB period.

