	Total	XX	XX
Cycle 3 Day 1	Decrease	xx (xx.x)	xx (xx.x)
•	No Change	xx (xx.x)	xx (xx.x)
	Increase	xx (xx.x)	xx (xx.x)
	Total	XX	XX

CFB=Change from Baseline

Baseline=Cycle 1 Day 1 (or Pre-Study if <= 3 days prior to Cycle 1 Day 1 or if value at Cycle 1 Day 1 is missing)

Percentages are calculated using the number of subjects in the Safety Population for each treatment as the denominator. Includes visits with at least 4 subjects in either treatment group

Source: Listing 16.2.9.3

Programming Note: Continue for all visits (Day 1 for all cycles) with at least 4 subjects in either treatment group.

Table 14.3.8

Vital Signs And Weight Safety Population

Parameter (Units)	Visit	Statistic	CF102 (N=xx)	Placebo (N=xx)
			,	, ,
Systolic BP (mmHg)	Pre-Study	n (OD)	XX	XX
		Mean(SD)	xxx.xx (xxx.xxx)	xxx.xx (xxx.xxx)
		Median	XXX.XX	XXX.XXX
		Min, Max	XXX.X, XXX.X	XXX.X, XXX.X
	Baseline	n	XX	XX
		Mean(SD)	xxx.xx (xxx.xxx)	xxx.xx (xxx.xxx)
		Median	xxx.xx	xxx.xxx
		Min, Max	XXX.X, XXX.X	XXX.X, XXX.X
	Cycle 1 Day 1			
	Hour 1	n	xx	XX
		Mean (SD)	xxx.x (xxx.xx)	xxx.x (xxx.xx)
		Median	xxx.x	xxx.x
		Min, Max	xxx, xxx	XXX, XXX
	CFB to	,	7001, 7001	7001, 7001
	Cycle 1 Day 1 Hour 1	n	XX	XX
	Cycle : Bay i riour i	Mean (SD)	xxx.x (xxx.xx)	xxx.x (xxx.xx)
		Median	XXX.X	XXX.X
		Min, Max	XXX, XXX	XXX, XXX

BP=Blood Pressure

BMI=Body mass index

CFB= Change From Baseline

Baseline=Cycle 1 Day 1 (or Pre-Study if <= 3 days prior to Cycle 1 Day 1 or if value at Cycle 1 Day 1 is missing)

Includes visits with at least 4 subjects in either treatment group

Source: Listings 16.2.9.1, 16,2.9.2

Programming Notes: Continue for Diastolic BP (mmHg), Pulse (beats/min), Temperature (deg C), Respiratory Rate (/min), Weight (kg), and BMI (kg/m2) and visits (Days 1 and 15 of each cycle, Day 8 of Cycle 1, and Hours 1, 2, 3, 4, 6 and 8 on Cycle 1 Day 1) with CFB. Weight (kg) is not recorded at Hours 1, 2, 3, 4, 6 and 8 on Cycle 1 Day 1. Include visits with at least 4 subjects in either treatment group.

Table 14.3.9.1 Electrocardiogram (ECG) Parameters Safety Population

_			CF102	Placebo
Parameter	Visit	Statistic	(N=xx)	(N=xx)
Heart Rate (bpm)	Pre-Study	n	XXX	XXX
(25)		Mean (SD)	xxx.x (xxx.xx)	xxx.x (xxx.xx)
		Median	XXX.X	XXX.X
		Min, Max	XXX, XXX	XXX, XXX
	Baseline	n	XXX	XXX
		Mean (SD)	xxx.x (xxx.xx)	xxx.x (xxx.xx)
		Median	XXX.X	XXX.X
		Min, Max	XXX, XXX	XXX, XXX
	Cycle 1 Day 1 Hour 2	n	XXX	XXX
		Mean (SD)	xxx.x (xxx.xx)	xxx.x (xxx.xx)
		Median	XXX.X	XXX.X
		Min, Max	XXX, XXX	XXX, XXX

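### Table 14.3.8 applies the 3-day Pre-Study baseline, which fits weight and BMI, to vital signs too, so its changes from baseline can differ from its source listing

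*SAP*

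**What the plan says.** The mock shells give two baseline rules for the same measurements.

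- **Listing 16.2.9.1 (Vital Signs):** "Baseline=Cycle 1 Day 1 (or Pre-Study if value at Cycle 1 Day 1 is missing". There is one trigger for going back to Pre-Study, a missing Day 1 value.
- **Table 14.3.8 (Vital Signs And Weight):** the parenthesis reads "or Pre-Study if <= 3 days prior to Cycle 1 Day 1 or if value at Cycle 1 Day 1 is missing". There are two triggers, joined by *or*.

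The table names its origin as "Source: Listings 16.2.9.1, 16,2.9.2", that is, the vital-signs listing together with the listing of weight, height and BMI. It reports changes at Hours 1, 2, 3, 4, 6 and 8 on Cycle 1 Day 1 for vital signs only; its programming note says that "Weight (kg) is not recorded at Hours 1, 2, 3, 4, 6 and 8 on Cycle 1 Day 1".

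On what is measured at Day 1, footnote d of Table 1-1 in the protocol (and its counterpart in the SAP) schedules "Temperature, pulse, respiration, blood pressure at: Pre-Study; pre-dose at all visits". SAP Section 7 sets baseline at Day 1 of Cycle 1 "unless the pre-study assessment was performed within 3 days prior to baseline", and adds that, where this exception applies, "assessments do not need to be repeated prior to initiation of dosing for Physical Examination, Body Weight, Clinical Laboratory testing, Pregnancy Test, and ECOG PS". Vital signs are not in that list; body weight is.

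**The concern.** A change at 1 to 8 hours after the first dose is most naturally read against the value taken just before that dose. For some subjects the table footnote, taken literally, replaces that value with one up to 3 days older, although the Day 1 pre-dose value is planned and available. The Baseline row then shows the Pre-Study value, and the Day 1 pre-dose value enters no row of the table. The same subject has one change in the listing and another in the table that claims to summarise it.

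Cycle 1 Day 1 is the only timed post-dose series of vital signs in the double-blind period, and Protocol Section 4.1 reports increased heart rate in monkeys at 60 mg/kg. The table should therefore measure acute change cleanly and agree with its source.

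**Working it through.** No figure in the plan needs reproducing. The check compares the rules and then does simple algebra.

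**1. The baseline rules side by side**

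| Output | Pre-Study used if 3 days or less before Day 1 | Pre-Study used if Day 1 missing |
|---|---|---|
| Table 14.3.8 (vital signs, weight, BMI) | yes | yes |
| Listing 16.2.9.1 (vital signs) | no | yes |
| Listing 16.2.9.2 (weight, BMI) | yes | yes |
| Table 14.3.9.1 and Listing 16.2.10.1 (ECG) | no | yes |

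The table matches its weight and BMI source but not its vital-signs source. ECG is also repeated pre-dose on Day 1, and its table and listing have no 3-day clause.

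**2. Which rule fits the schedule**

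- In Table 1-1 of both documents, vital signs carry footnote d (pre-dose at every visit). Body weight on Day 1 carries footnote c (no repeat needed if done within 3 days).
- Protocol Section 9.3.2 attaches the 3-day waiver to the physical examination, laboratory tests, pregnancy test and ECOG PS. The vital-signs entry has no waiver.
- SAP Section 6 ties the 3-day baseline to footnotes a and c only.
- SAP Section 7 takes the change from Screening only where Screening was the last pre-treatment assessment. With a Day 1 pre-dose value recorded, it was not.
- SAP Section 8 substitutes Pre-Study only for a Baseline value that is missing because it was not repeated.

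All of these point to the Day 1 pre-dose value for vital signs.

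**3. Difference per subject**

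Let P be the Pre-Study value, D the Day 1 pre-dose value and Y any later value. For a subject with P taken 3 days or less before Day 1 and D recorded:

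change in table − change in listing = (Y − P) − (Y − D) = D − P.

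For every other subject the difference is 0. It applies at every later time point, not only Hours 1 to 8.

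**4. Difference in a group mean**

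Let f be the share of summarised subjects affected. The mean change moves by f × mean(D − P) among those subjects. The documents give neither quantity. By assumption only, with mean(D − P) = 5 mmHg:

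- f = 0: 0 × 5 = 0 mmHg
- f = 10%: 0.10 × 5 = 0.5 mmHg
- f = 50%: 0.50 × 5 = 2.5 mmHg

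**5. Difference between arms**

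Protocol Section 7.3 randomises on Day 1 under double-blind conditions, so P and D both precede dosing. In expectation, f and mean(D − P) are the same for CF102 and placebo, and the shift cancels in a comparison. What remains is extra variability.

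**6. After the fix**

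If the vital-sign rows use the listing's rule, both changes equal Y − D when D is recorded and Y − P when it is missing. The table-listing difference is then 0 for every subject.

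**The case against.** **The SAP text already gives the right rule.** Sections 6, 7 and 8, the source listing and the ECG shell all lead to Day 1 pre-dose, so a programmer working from them would not go wrong. It would be too strong to infer that post-dose changes will be taken from the wrong day; that happens only if the table footnote is followed over the text. This stands as a limit. It does not make the footnote harmless: Section 2 of the mock shells says that variables under the 3-day rule are identified by just such a footnote, so following it would be a reasonable reading.

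**The footnote might be read as applying only when Day 1 is missing.** That would remove the conflict, but the footnote gives the missing value as a separate alternative. Nor does it help to read the opening sentence of SAP Section 7 as a general 3-day rule. The next sentence confines it to named assessments, and a general rule would put Listing 16.2.9.1 and the ECG outputs in error instead.

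**The heart-rate question is largely covered elsewhere.** A reader might infer that an acute heart-rate effect could be missed. Table 14.3.9.1 summarises ECG heart rate at 2, 4 and 6 hours on Cycle 1 Days 1 and 8 against Day 1 Hour 0. What depends on Table 14.3.8 alone is blood pressure, respiration and temperature, and pulse at 1, 3 and 8 hours.

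**No data are lost.** Listing 16.2.9.1 prints both the Pre-Study and the Day 1 values, so any difference can be traced.

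**The size is unknown.** One could put a figure on the added spread with SD × √(2(1 − r)). With an assumed pulse SD of 10 bpm, r = 0.75 to 0.85 within a day gives 7.1 to 5.5 bpm; r = 0.5 to 0.6 across days gives 10.0 to 8.9 bpm. The increase is 26% to 83% over all combinations. The documents support none of these inputs, so the range illustrates the direction and is not an estimate of impact.

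**Conclusion.** The Table 14.3.8 footnote is a wrong derivation rule for its vital-sign rows and conflicts with the listing it cites. It is right for weight and BMI. Each affected subject's change differs from the listing by D − P, and a group mean moves by f × mean(D − P). The affected group is subjects with Pre-Study 3 days or less before Day 1 and a recorded Day 1 value; its size is not given and may be zero.

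The consequence is limited. SAP Section 7.7.4 plans descriptive statistics only for vital signs, with no test or decision rule. A reader might infer a bias between arms, but the documents do not support that, since both candidate baselines precede dosing in a randomised, blinded trial. No efficacy result is touched. The conclusion assumes that vital signs were taken pre-dose on Day 1 as scheduled and that the footnote is programmed as written. It is a small, definite inconsistency in a safety output and should be corrected.

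**What to change.** Split the baseline footnote of Table 14.3.8:

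- **Blood pressure, pulse, respiration, temperature:** baseline is the Cycle 1 Day 1 pre-dose value; use Pre-Study only if that value is missing.
- **Weight and BMI:** keep the 3-day clause as it stands.

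Add one sentence to SAP Section 7.7.4 naming the vital-sign baseline, so that the opening of Section 7 cannot be read as overriding it. Listings 16.2.9.1 and 16.2.9.2 need no change.

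The cost is one footnote, one derivation line and one sentence, using data already scheduled for collection. If the table has already been produced under the 3-day rule, rerun it and record the change in the clinical study report, as SAP Section 9 provides for changes not covered in the SAP.
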